DBE	dose blinded extension
DBP	diastolic blood pressure
EC ₅₀	Concentration at 50% of maximum observed biologic effect
ECG	electrocardiogram
eCRF	electronic case report form
EOS	end of study
EOT	end of treatment
EP-RPS	Early Parkinson's Region Progression Score
██████	██
ER	exposure-response
██████	██
██████	██
ICF	informed consent form
ICH	International Conference on Harmonisation
IDMC	independent data monitoring committee
INR	International normalized ratio
ITT	intent-to-treat

CONFIDENTIAL

The information contained herein may not be used, disclosed, or published without the written consent of Biogen MA Inc.

IXRS	Interactive Voice/Web Response System
LE	Lower Extremity
LOCF	last observation carried forward
█	█
LSmeans	least-square means
IV	intravenous
mAb	monoclonal antibody
MAO-B	monoamine oxidase type B
█	█
MCP-MOD	multiple comparison procedure – modeling
MDS-UPDRS	Movement Disorder Society Sponsored Revision of the Unified Parkinson’s Disease Rating Scale
MedDRA	Medical Dictionary for Regulatory Activities
MMRM	mixed-model repeated measures
█	█
MRI	magnetic resonance imaging
█	█
PCS	potentially clinically significant
PD	Parkinson’s disease
█	█
PIGD	Postural Instability Gait Difficulty
PK	pharmacokinetic(s)
PT	preferred term
PP	per-protocol
█	█
RBC	red blood cell
RNA	ribonucleic acid
SAE	serious adverse event
SAP	statistical analysis plan
SBP	systolic blood pressure
SBR	striatal binding ratio
█	█
SD	standard deviation
SE	standard error
█	█
SOC	system organ class
SPECT	single-photon emission computed tomography
TEAE	treatment-emergent adverse event
TD	Tremor Dominant
█	█
ULN	upper limit of normal
US	United States
WBC	white blood cell
WHO	World Health Organization
█	█

CONFIDENTIAL

The information contained herein may not be used, disclosed, or published without the written consent of Biogen MA Inc.

1 SCOPE OF WORK IN THE STATISTICAL ANALYSIS PLAN

This statistical analysis plan (SAP) only covers the analyses for the placebo-controlled portion of the study (Year 1). Hereafter, the placebo-controlled portion of the study will be referred to as “the study” in the rest of this SAP (e.g., completion of the study means completion of the placebo-controlled portion). A separate SAP will be prepared for the analyses of the dose-blinded extension period and integrated analyses across both portions of the study.

2 DESCRIPTION OF OBJECTIVES AND ENDPOINTS

The objectives and endpoints of the study are listed below.

The secondary efficacy endpoints have been ranked based on the order of clinical importance.

Primary Objective	Primary Endpoints
To evaluate the clinical efficacy of BIIB054 via dose response using the change from baseline in Movement Disorder Society-Unified Parkinson's Disease Rating Scale (MDS-UPDRS) Total Score	Change from baseline in MDS-UPDRS Total Score (Sum of Parts I, II, and III) at the primary timepoints of Week 52 and Week 72
Secondary Objectives	Secondary Endpoints
To evaluate the clinical efficacy of BIIB054 based on MDS-UPDRS subparts	Change from baseline to Week 52 in MDS-UPDRS the subparts III, II and I (each part separately)
	Change from baseline to Week 72 and end of study in MDS-UPDRS the subparts III, II and I (each part separately)
To assess the PK profile of BIIB054	Concentration of BIIB054 in the serum
To evaluate the dose-related safety of BIIB054	Incidence of adverse events (AEs) and serious adverse events (SAEs)
To evaluate the pharmacodynamic effects of BIIB054 on the integrity of nigrostriatal dopaminergic nerve terminals	Change from baseline to Week 52 in striatal binding ratio (SBR) in the putamen, striatum, and caudate as measured by single-photon emission computed tomography (SPECT) imaging of the dopamine transporter (DaT) with ioflupane I123 (DaTscan™)

CONFIDENTIAL

The information contained herein may not be used, disclosed, or published without the written consent of Biogen MA Inc.

To evaluate the immunogenicity of BIIB054	Incidence and titer of anti-BIIB054 antibodies in the serum
Exploratory Objectives	Exploratory Endpoints

[Redacted]
	
[Redacted]
 
 • [Redacted] • [Redacted] • [Redacted] • [Redacted] • [Redacted] - [Redacted] - [Redacted] - [Redacted] • [Redacted]
	
[Redacted]

	[REDACTED]
	[REDACTED]
	[REDACTED] • [REDACTED] • [REDACTED]
	[REDACTED] • [REDACTED] • [REDACTED] • [REDACTED] [REDACTED] • [REDACTED] - [REDACTED] - [REDACTED]

[REDACTED]	[REDACTED]
[REDACTED]	[REDACTED]
[REDACTED]	[REDACTED]
[REDACTED]	[REDACTED]
[REDACTED]	[REDACTED]
[REDACTED]	[REDACTED]
[REDACTED]	[REDACTED]

CONFIDENTIAL

The information contained herein may not be used, disclosed, or published without the written consent of Biogen MA Inc.

[REDACTED]
	
[REDACTED]
 
• [REDACTED]• [REDACTED]• [REDACTED]• [REDACTED]• [REDACTED]

[REDACTED]
	
[REDACTED]
 
• [REDACTED]• [REDACTED]• [REDACTED]

3 STUDY DESIGN

3.1 Study Overview

This Phase 2a, randomized, double-blind, parallel-group, placebo-controlled study (Year 1) with an active-treatment dose-blinded period (Years 2 through 4) will examine the efficacy, safety, PK, and pharmacodynamics of BIIB054, administered every 4 weeks via IV infusion

CONFIDENTIAL

The information contained herein may not be used, disclosed, or published without the written consent of Biogen MA Inc.

to adult subjects with PD. Approximately 311 subjects will be enrolled at about 85 sites globally.

3.1.1 Year 1 (Placebo-Controlled Portion of the Study)

Prior to the first dose in Year 1, all subjects in the study will be randomized into 4 arms, to receive 13 doses of BIIB054 (250, 1250, or 3500 mg) or placebo.

Subjects will be enrolled into 2 cohorts. Cohort A will be randomized first, in a 1:1:1:1 ratio into each of the 4 treatment arm and will include approximately 24 subjects. Randomization and dosing for Cohort B (approximately 287 planned subjects) will start after all subjects in Cohort A complete Week 12 assessments, and all available safety and PK data are reviewed by the IDMC. Randomization of subjects in Cohort B will be stratified by baseline (Day 1) MDS-UPDRS Part I + II + III total scores (≤ 35 and > 35) and striatum SBR (≤ 1.2 and > 1.2), and subjects will be randomized at Day 1 into 1 of 4 parallel dosing arms in each stratum.

After all subjects in Cohort A complete Week 12 assessments (28 days after their third infusion), and before dosing any subjects in Cohort B, all available safety and PK data will be reviewed by the IDMC. No subjects in Cohort B may be dosed until the IDMC review is complete. The study schematic is presented in [Figure 1](#). After IDMC review is complete, subjects in Cohort B will be randomized, and dosing may begin. During the review period, subjects in Cohort A will continue to be dosed on a schedule of once every 4 weeks.

The first IDMC meeting will occur after the last subject in Cohort A completes Week 12 assessments, or approximately 6 months after the first subject has been enrolled in Cohort A, whichever comes first. Regular IDMC meetings will occur approximately every 3 months after the first meeting.

[REDACTED]

The Week 48 infusion is the last infusion of the placebo-controlled period, and Week 52 is the first dosing of the Dose-blinded portion of the study.

3.1.2 Years 2 Through 4 (Active-Treatment Dose-Blinded Portion of the Study)

Prior to Infusion 14 (the first dose of Year 2) at Week 52, subjects who received placebo in Year 1 will be randomized into 1 of the active-dosing arms for Year 2; these subjects will receive BIIB054 in Year 2. Subjects who received BIIB054 (1250 mg or 3500 mg) in Year 1 of the study will continue with the same dose regimen in Year 2. Subjects receiving the 250-mg dose in Year 1 continued on their original dose assignment.

Subjects will receive 12 additional doses of BIIB054 (250, 1250, or 3500 mg) in Year 2 and up to 16 additional doses in Years 3 and 4. Up until the last subject in the study has had his or her last dose in Year 2 of the study (Week 96 Visit), eligible subjects will be able to continue treatment once every 4 weeks.

Subjects who complete dosing through Week 96 and the Final Visit 12 weeks after the last visit will be considered Year 2 completers in the eCRF.

CONFIDENTIAL

[figure not shown]
The information contained herein may not be used, disclosed, or published without the written consent of Biogen MA Inc.

See Figure 2 for a depiction of the duration of dosing in Years 3 and 4 for subjects continuing dosing past Week 96.

Figure 4 on protocol presents a flowchart for dosing and procedures from Week 96 through end of study, including how to determine which subjects are eligible to continue dosing past Week 96.

3.2 Study Schematic

[figure not shown]
Figure 1: Study Design

DaT = dopamine transporter; IDMC = independent data monitoring committee; PK = pharmacokinetic(s); SPECT = single-photon emission tomography

* Prior to Infusion 14 (first dose of Year 2), subjects who received placebo in Year 1 will be randomized to 1 of the active-treatment groups to receive BIIB054 in Year 2. Subjects who received BIIB054 in Year 1 will continue with the same dose regimen in Years 2 through 4. The last subject in the study has had his or her Week 96 Visit. Not all subjects will have the opportunity for dosing past Year 2/Week 96.

Figure 2: Overview of Study Dosing:

Q4W = every 4 weeks.

Year 1 = Placebo-controlled period. Years 2 through 4 = Active-treatment dose-blinded period. Not all subjects will have the opportunity for dosing

CONFIDENTIAL

The information contained herein may not be used, disclosed, or published without the written consent of Biogen MA Inc.

3.3 Schedule of Events

See Protocol Section 4.2.

4 SAMPLE SIZE JUSTIFICATION

The sample size calculation is based on changes in MDS-UPDRS Part I + II + III total score at Week 52 and at Week 72 of treatment. Based on data from the Parkinson's Progression Markers Initiative study, the placebo subject's mean and standard deviation (SD) at Week 52 and Week 72 are assumed to be 8.0 (10.64) and 9.6 (13.7) respectively. Assuming a maximum of 55% reduction in the change from baseline in the active group with maximum response relative to placebo group, the mean (SD) for this active group will be 3.2 (10.64) and 3.84 (13.7) respectively at Week 52 and Week 72, and the responses for other active groups are assumed to be somewhere between 0 and the maximum response. The primary analysis will be based on the MCP-MOD method to detect a dose-response trend while controlling for multiplicity. Optimal contrasts will be constructed to detect potential dose-response trend under common dose-response curves (e.g., E_{max} , exponential, logistic, linear in log dose, and quadratic model, which are illustrated with parameters shown in [Figure 4.1](#) which will be used for both Week 52 and Week 72). The planned enrollment is 311 subjects total (24 subjects in Cohort A and 287 subjects in Cohort B, [4.1](#)). Actual enrollment is 357 subjects. In Cohort A, 29 subjects were randomized in a 1:1:1:1 ratio to each of the treatment groups, while in Cohort B 328 subjects were randomized in 2:1:2:2 ratio to the placebo, 250 mg, 1250 mg, and 3500 mg groups. Based on the actual enrollment, the estimated number of subjects by cohort and treatment groups are given in [Table 4.4.2](#) below. After accounting for dropout rate of 10% and 15% at Week 52 and Week 72, respectively, the estimated sample sizes are given in [Table](#) and [Table 1](#). With the updated sample size, the study will provide an average power of approximately 80% to detect the dose-response trend over 1 year of treatment, based on a 2-sided type I error of 0.05 and approximately 73% of power at the Week 72 analyses, based on a 2-sided type I error of 0.05. Overall, the sample size in the study will provide approximately 89% power, taking into consideration success at either Week 52 or Week 72. The final candidate models for the MCP-MOD are prespecified and described below.

With an estimated sample size of 100 subjects dosed per arm in the 1250 mg and 3500 mg arms, the study has 80% probability of detecting AEs with a rate of 1.6% or greater in these 2 arms, and a 90% probability of detecting AEs occurring with a rate of 2.3% or greater.

Table 4.1: Estimated Sample Size Per Group (Planned)

	Treatment Group				Total
	Placebo	BIIB054 250 mg	BIIB054 1250 mg	BIIB054 3500 mg	
Cohort					
Cohort A	6	6	6	6	24
Cohort B	82	41	82	82	287
Total	88	47	88	88	311

Table 4.2: Estimated Sample Size Per Group Based on Actual Enrollment (Before Drop-Outs)

	Treatment Group				Total
	Placebo	BIIB054 250 mg	BIIB054 1250 mg	BIIB054 3500 mg	
Cohort					
Cohort A	8	7	7	7	29
Cohort B	93	47	94	94	328
Total	101	54	101	101	357

Table 4.3: Estimated Sample Size Per Group Based on Actual Enrollment (After Adjusting for 10% Drop-Out At Week 52)

	Treatment Group				Total
	Placebo	BIIB054 250 mg	BIIB054 1250 mg	BIIB054 3500 mg	
Cohort					
Cohort A	7	6	6	6	25
Cohort B	84	42	84	84	294
Total	91	48	90	90	319

[figure not shown]
Table 1: Estimated Sample Size Per Group Based on Actual Enrollment (After Adjusting for 15% Drop-Out At Week 72)

	Treatment Group				Total
	Placebo	BIIB054 250 mg	BIIB054 1250 mg	BIIB054 3500 mg	
Cohort					
Cohort A	7	6	6	6	25
Cohort B	79	40	80	80	279
Total	86	46	86	86	304

CONFIDENTIAL

The information contained herein may not be used, disclosed, or published without the written consent of Biogen MA Inc.

Figure 4.1: Candidate Models for Dose-Response

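### The planned maximum effect is stated as a 55% reduction, but the active-arm means printed beside it (3.2 and 3.84) are a 60% reduction; the stated 80% and 73% power fit 55%

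*SAP*

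**What the plan says.** Year 1 SAP, Section 4 (Sample Size Justification), gives the mean change (SD) in MDS-UPDRS Parts I+II+III on placebo at Weeks 52 and 72; these "are assumed to be 8.0 (10.64) and 9.6 (13.7) respectively". The planning effect follows: "Assuming a maximum of 55% reduction in the change from baseline in the active group with maximum response relative to placebo group". The same sentence continues: "the mean (SD) for this active group will be 3.2 (10.64) and 3.84 (13.7) respectively at Week 52 and Week 72".

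Three power figures rest on these inputs:

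- Week 52, two-sided 0.05: "the study will provide an average power of approximately 80% to detect the dose-response trend over 1 year of treatment"
- Week 72: "approximately 73% of power at the Week 72 analyses, based on a 2-sided type I error of 0.05"
- Overall: "approximately 89% power, taking into consideration success at either Week 52 or Week 72"

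The Week 52 and Week 72 figures are tied to the updated sample size, based on the 357 subjects actually enrolled. The tables that follow reduce it for 10% dropout at Week 52 and 15% at Week 72. Section 3 of the extension SAP repeats the same effect, means and powers.

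**The concern.** The percentage and the means describe the same quantity and should agree by a single multiplication. They do not, at either timepoint. Rounding cannot explain it: 3.84 is printed to two decimals and is exactly 0.40 of 9.6. The sentence is intact, nothing in it is blacked out, and it recurs in the second SAP.

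This is the effect on which the sample size for the primary endpoint rests. Anyone repeating the calculation from the means obtains powers that differ from the stated ones. Anyone judging later what a null result rules out would use 4.8 and 5.76 points as the effects the trial had 80% and 73% power to detect.

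**Working it through.** **The contradiction.** From the printed means:

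- Week 52: 3.2 / 8.0 = 0.40, so the reduction is 60% and the difference is 8.0 − 3.2 = 4.80 points.
- Week 72: 3.84 / 9.6 = 0.40, so the reduction is 60% and the difference is 9.6 − 3.84 = 5.76 points.

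From the stated 55%:

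- Week 52: 8.0 × 0.45 = 3.60, difference 4.40 points.
- Week 72: 9.6 × 0.45 = 4.32, difference 5.28 points.

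**Which value gives the stated power.** Inputs, all from the Year 1 SAP:

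- SD 10.64 (Week 52) and 13.7 (Week 72), Section 4.
- Post-dropout subjects on placebo / 250 / 1250 / 3500 mg: 91/48/90/90 = 319 at Week 52 and 86/46/86/86 = 304 at Week 72, tables in Section 4.
- Two-sided alpha 0.05, Section 4.
- Candidate models, Appendix III: Emax (ED50 450.5), exponential (2850.5), logistic (1547.5, 510.5), linear-log (offset 237.5), quadratic (−0.0002), exponential (860.5) and linear. Section 4 names five types; both the seven-model and five-model sets were run.

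Method: for each model, the optimal contrast across the four arms was formed. The largest contrast statistic was compared with its multivariate-t critical value (about 2.25 for seven models, 2.21 for five). Power was found by simulation with each model in turn taken as true, and then averaged. Each curve's maximum over the 0 to 3500 mg range was set to the planning effect.

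| Maximum effect | Models | Week 52 | Week 72 |
|---|---|---|---|
| Stated in the SAP | not given | about 80% | about 73% |
| 55% (4.40 / 5.28) | 7 | 81.4% | 73.6% |
| 55% (4.40 / 5.28) | 5 | 80.8% | 73.0% |
| 60% (4.80 / 5.76) | 7 | 87.6% | 80.8% |
| 60% (4.80 / 5.76) | 5 | 87.2% | 80.2% |

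The stated figures are reproduced within 2 points at 55%. At 60% they are missed by 7 to 8 points at both timepoints.

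**Cross-check without simulation.** Placebo against the best dose, normal approximation, power = Φ(difference / SE − 1.96):

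- Week 52, 90 per arm: SE = 10.64 × √(2/90) = 1.586. For 4.40, Φ(2.774 − 1.96) = 79.2%. For 4.80, Φ(3.026 − 1.96) = 85.7%.
- Week 72, 86 per arm: SE = 13.7 × √(2/86) = 2.089. For 5.28, Φ(2.527 − 1.96) = 71.5%. For 5.76, Φ(2.757 − 1.96) = 78.7%.

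This points the same way: 55% falls near 80% and 73%, and 60% does not.

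**The case against.** Nobody can dispute that 55% and the printed means disagree. What can be disputed is whether the power figures prove that 55% was used, and how much it matters.

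- **Scaling of the quadratic curve.** With parameter −0.0002 its peak is at 1 / (2 × 0.0002) = 2500 mg, which is not a tested dose. Its value at 3500 mg is 3500 − 0.0002 × 3500² = 1050, against 1250 at the peak. Section 4 assigns the maximum to an active group, so scaling over tested doses is a fair reading. It gives 83.4% / 76.0% at 55%, about 3 points high. This stands as a limit on how exact the match is, but on the same reading 60% gives 89.3% / 82.8%, which is further off.
- **Other routes to about 80% / 73% at 60%.** With the planned 311 less dropout, 60% gives 82.9% / 75.0% at alpha 0.05, and 80.5% / 72.0% at alpha 0.04 (seven models). With the updated sample size, the lowest power over the models, rather than the average, is 80.0% / 72.1%. Each route contradicts Section 4, which specifies the updated sample size, alpha 0.05 and, at Week 52, average power. Power figures left over from an earlier calculation remain possible but have no support in the text.
- **The 89% overall figure.** It does not discriminate. It depends on the correlation between Week 52 and Week 72, which the plan does not give, and on the alpha split. With scaling over tested doses, 55% reaches 89% at a correlation near 0.7 if 0.05 is used at each timepoint, or near 0.2 to 0.3 with the 0.04/0.01 split; 60% reaches it near 0.7 to 0.8 with that split.
- **Consequence.** Enrolment is complete at 357, and the size of the maximum effect enters no model, contrast, alpha or decision rule. Neither value hides an underpowered trial: if 60% is right, the stated power is too low. This stands and limits the seriousness.

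**Conclusion.** The contradiction is exact at both timepoints and needs no simulation: a 55% reduction is stated and a 60% reduction is printed. At the stated sample sizes, SDs and two-sided 0.05, the 80% and 73% fit 55% and not 60%, so the printed means are very likely the error. The gap is 0.40 points in the Week 52 mean (3.60 − 3.2) and 0.48 in the Week 72 mean (4.32 − 3.84), worth about 6 to 7 points of power at each timepoint.

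The attribution to 55% rests on the averaged MCP-Mod calculation with the listed models; the match is within 2 points if each curve is scaled over the dose range and about 3 points high if scaled over tested doses only. It applies to the 80% and 73% figures, not to the 89%. The error is substantive because it concerns the central planning input, but it changes no analysis, and the sample size can stand.

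**What to change.** In Section 4 of the Year 1 SAP and Section 3 of the extension SAP, keep 55% and replace the active means by 3.60 (Week 52) and 4.32 (Week 72). The sponsor should first confirm from its own calculation that 55% produced the stated powers.

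If 60% was the actual assumption, keep the means, change the percentage in both SAPs, restate the powers at two-sided 0.05 as about 88% and 81%, and recompute the overall figure. In either case, one sentence giving the correlation and alpha levels behind the 89% would make that figure checkable.

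The cost is wording only: no change to enrolment, model, contrasts or testing procedure.

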5.3.2 MDS-UPDRS

5.3.2.1 Primary efficacy endpoint

Estimand:

The estimand of the primary analysis is the mean difference of the change from baseline in MDS-UPDRS I+II+III total score at Week 52 between treatment groups in the ITT population in a hypothetical setting where subjects do not start PD medication. MDS-UPDRS data collected after the intercurrent events, i.e., subjects start PD medication will be excluded in the primary analysis. Specifically, the estimand takes the following into consideration:

- A. Population: ITT population as defined in Section 5.1.2
- B. Variable: change from baseline to Week 52 in MDS-UPDRS score
- C. Intercurrent events: had PD medication not been made available to subjects prior to Week 52
- D. Population-level summary: difference in variable means between treatment conditions.

CONFIDENTIAL

The information contained herein may not be used, disclosed, or published without the written consent of Biogen MA Inc.

MMRM will be used as the primary analysis to analyze the change from baseline in MDS-UPDRS score. The model includes the fixed effects of treatment group, time (categorical), baseline PD subtype (categorical; PIGD vs TD vs indeterminate), prior use of PD medication (categorical), treatment group-by-time interaction, region (categorical), baseline MDS-UPDRS I+II+III total (continuous), baseline MDS-UPDRS I+II+III total by time interaction and baseline striatum SBR values (continuous), and baseline striatum SBR by time interaction. A random intercept and slope will be included in the model to model the random effects within subjects. If small sample size in subgroups of PD types causes lack of model convergence, the indeterminate group will be combined with the TD group. The Kenward-Roger approximation will be used to estimate the denominator degrees of freedom. Least square means (LSmeans) of each treatment group as well as treatment difference between BIIB054 groups and placebo will be displayed with 95% CI and p-value at Week 52. If the distribution of the outcome is highly skewed, p-value will be generated from the MMRM model based on ranked data. In the primary analysis, missing data are assumed to be missing at random (Rubin 1976), and MDS-UPDRS I+II+III score is impacted by PD medication.

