A multiple comparison adjustment method will be applied to control the overall type I error at 0.05 in the study, due to the primary endpoint of change from baseline in MDS-UPDRS total score being analyzed at Week 52 and Week 72, and superiority against placebo is considered reached in the study if statistically significant result is achieved at either timepoint at the respective adjusted alpha-level.

An improved fall-back procedure will be used to control the overall type I error at 0.05 level due to multiple-testing. An alpha of 0.04 will be allocated to the Week 52 primary endpoint analyses and an alpha of 0.01 will be allocated to the Week 72 primary endpoint analysis.

- If the Week 52 analysis is statistically significant at the 0.04 level (i.e. p-value ≤ 0.04), the alpha of 0.04 will be transferred (recycled) to the Week 72 analysis, and Week 72 will have alpha=0.05.
- If the Week 52 analysis is not statistically significant at the 0.04 level, alpha of 0.01 will be used for the Week 72 analysis. Statistical significance is considered achieved if the p-value is ≤ 0.01 at Week 72.
- If statistical significance is achieved at the Week 72, in either scenarios above, then the alpha of 0.01 will be transferred (recycled) back to Week 52, and the Week 52 primary analysis will be re-evaluated for statistical significance at the 0.05 level. This will only change the conclusion of the Week 52 results if the initial p-value is greater than 0.04 and ≤ 0.05 .

No additional multiplicity adjustments will be made for secondary or [REDACTED] endpoint analyses.

A blinded sample size re-estimation may be conducted when approximately 10% of subjects have completed the Week 52 Visit or approximately 1 month before enrollment is projected to be completed, whichever is earlier (description of method is below). The study sample size may be increased based on this blinded data review. There may be small adjustments to the percentage depending on actual enrollment rate. As of the finalization of protocol Version 8 (Aug 2020), all subjects have completed Week 52 visits, this analysis was not conducted.

Blind sample size re-estimation

The sample size for this study may be reassessed in a blinded manner in a cutoff date of February 2020, by which time approximately 78/311 (25%) of subjects will complete the Week 52 visit.

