A multiple comparison adjustment method (graphical procedure) will be applied to control the overall type I error at 0.05 in the study, due to the primary endpoint of MDS-UPDRS total score being analyzed at Week 52 and Week 72, and superiority against placebo is considered reached in study if statistically significant result is achieved at either timepoint. Please refer to the “Interim Analysis” section for this method. Pairwise comparison of each active group versus delayed-start group(s) will also be conducted, however, no additional multiplicity adjustment will be made, and nominal p-values will be reported. The primary comparison is between each of the early-start BIIB054 dose group, with the pooled delayed-start BIIB054 group.

The following three comparisons will be evaluated for the long-term efficacy analyses of BIIB054:

- The early start 250 mg compared with the pooled delayed start group;
- The early start 1250 mg compared with the pooled delayed start group;
- The early start 3500 mg compared with the pooled delayed start group

The following comparisons may also be evaluated:

- The early start 250 mg compared with the delayed start 250 mg;
- The early start 1250 mg compared with the delayed start 1250 mg.
- The early start 3500 mg compared with the delayed start 3500 mg.

Per design, a subset of subjects will enter year 3 and 4 for a limited time. There will be some visits with too few data in year 3 and 4. If this is the case, the visits with too few data will be excluded from the MMRM analyses, Otherwise, the MMRM model will not converge. In addition, since most patients will start PD medication by year 1, most data in year 2-4 will be after PD medication. Therefore, data after subject start PD medication will be included in the MMRM analyses. Otherwise, the MMRM model will not converge.

Data at the common visits of cohort A and cohort B will be included in the by visit summary and MMRM model. Data at all visits will be listed.

CONFIDENTIAL

The information contained herein may not be used, disclosed, or published without the written consent of Biogen MA Inc.

	Statistical Analysis Plan Dose Blinded Extension Period	V2.0
---	---	-------------

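### The Week 52 power of about 80% allows for 10% dropout only, although the primary analysis also removes all data after PD medication starts; the power is overstated by an amount the plan does not let one fix.

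*SAP*

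**What the plan says.** **Sample size (Year 1 SAP, Section 4).** The placebo means and SDs at Weeks 52 and 72 "are assumed to be 8.0 (10.64) and 9.6 (13.7) respectively". The effect is set by "Assuming a maximum of 55% reduction in the change from baseline in the active group with maximum response relative to placebo group". The only loss deducted is dropout: "After accounting for dropout rate of 10% and 15% at Week 52 and Week 72, respectively, the estimated sample sizes are given". Table 4.3 then shows 91, 48, 90 and 90 subjects at Week 52, 319 in all. On that basis "the study will provide an average power of approximately 80% to detect the dose-response trend over 1 year of treatment", at a two-sided 0.05. An overall power of about 89% is quoted for success at either Week 52 or Week 72.

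**Primary analysis (Year 1 SAP, Section 5.3.2.1).** The Week 52 estimand is hypothetical: "MDS-UPDRS data collected after the intercurrent events, i.e., subjects start PD medication will be excluded in the primary analysis". The table in Section 5.3.2.3 confirms that post-medication data enter only the sensitivity analysis. The model is an MMRM with random intercept and slope, under missing at random.

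**How many start, and when (extension SAP).** Section 4.3.2 says "since most patients will start PD medication by year 1, most data in year 2-4 will be after PD medication", and Section 4.6.2 repeats it. Section 4.3.1 of the same SAP instead refers to the majority taking PD medication after Week 52. No percentage appears in the readable text of either SAP.

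**Alpha (Year 1 SAP, Section 6).** "An alpha of 0.04 will be allocated to the Week 52 primary endpoint analyses". The remaining 0.01 goes to Week 72, with recycling in both directions.

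**The concern.** Table 4.3 counts subjects still in the study at Week 52. The primary analysis uses only values recorded before PD medication. A subject who starts medication at Week 30 and attends Week 52 counts in full in Table 4.3 but gives the primary analysis no Week 52 value. The power therefore belongs to a larger dataset than the one the primary estimand keeps.

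The Week 52 test carries 0.04 of the 0.05 alpha. A non-significant result would be read against 80% power that the retained data may not provide. The Week 52 estimate would also lean more on the missing-at-random assumption than Section 4 suggests. The 89% overall figure inherits the problem.

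**Working it through.** **Inputs.** From Year 1 SAP Section 4: SD 10.64; n = 91/48/90/90; maximum effect 55% of 8.0 = 4.4 points; two-sided 0.05. From Appendix III: seven candidate shapes over doses 0, 250, 1250 and 3500 mg.

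**Method.** For each shape the expected means μ are scaled so that the maximum over the dose range is 4.4. The optimal contrast is cᵢ ∝ nᵢ(μᵢ − μ̄), with μ̄ the n-weighted mean. The statistic is Z = Σcᵢȳᵢ / (SD·√Σ(cᵢ²/nᵢ)). The critical value is the 95th percentile of the largest |Z| under no effect, by simulation with known variance. Power is averaged over the shapes.

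**Step 1: reproduce the plan.** With no medication loss, power is 0.820 on seven shapes and 0.814 on the five named in Section 4, against about 80% stated. At Week 72 (n = 86/46/86/86, 55% of 9.6 = 5.28 points, SD 13.7) it is 0.743 and 0.736, against 73% stated. The plan's figures therefore match dropout as the only loss.

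A hand check for one pair (91 against 90): 4.4 / (10.64·√(1/91 + 1/90)) = 2.78, and Φ(2.78 − 1.96) = 0.79.

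The printed active mean of 3.2 is a 4.8-point difference, or 60%, which disagrees with the stated 55%. It gives 0.88 and does not reproduce 80%, so 4.4 is the basis used here.

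**Step 2: remove post-medication data.** Let f be the share of the 319 who start before their Week 52 assessment. The values of f are assumptions. If starters contribute nothing, each n is multiplied by (1 − f). If the model recovers half of their information, each n is multiplied by (1 − f/2).

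| f | No recovery, 0.05 | Half recovery, 0.05 | No recovery, 0.04 | Half recovery, 0.04 |
|---|---|---|---|---|
| 0 | 0.82 | 0.82 | 0.79 | 0.79 |
| 20% | 0.73 | 0.78 | 0.69 | 0.74 |
| 30% | 0.67 | 0.75 | 0.63 | 0.72 |
| 50% | 0.53 | 0.70 | 0.49 | 0.66 |
| 60% | 0.44 | 0.67 | 0.40 | 0.63 |

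The entries move by about 0.01 with the simulation run and the set of shapes. The 30% no-recovery and 60% half-recovery cases share the multiplier 0.70, hence the same power of 0.66 to 0.67. At 10% with no recovery, power at 0.05 is 0.78.

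**Step 3: separate the alpha effect.** Moving from 0.05 to 0.04 costs about 3 to 4 points in each row (for example 0.820 to 0.793, and 0.526 to 0.487). This is a different issue from medication loss. The stated 80% is at 0.05, so the 0.05 columns are the like-for-like comparison.

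**Step 4: is half recovery reasonable?** Assume visits every 8 weeks to Week 48 plus Week 52, and split the variance into intercept, slope and residual shares of 20/50/30, 10/40/50 or 20/65/15. Starts are either spread over the year or late, with the last unmedicated visit at Week 32, 40 or 48. The information kept at 50% starting is then 0.56 to 0.80 of full, with power 0.57 to 0.73 at 0.05. At 60% starting, power is 0.49 to 0.69. With starts spread over the year, power is 0.74 to 0.77 at 20% and 0.69 to 0.75 at 30%. Half recovery is thus plausible but lies towards the favourable side.

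**The case against.** **The start rate is unknown.** This stands. A reader might infer from Section 4.3.2 of the extension SAP that more than half of the Week 52 values are lost, several times the planned 10%, and that true power is near 50%. The documents do not support that. The sentence explains why Years 2 to 4 data are kept and gives no rate, and Section 4.3.1 words the timing as after Week 52. If most starts fall at or after the Week 52 assessment, the loss is much smaller; at about 10% the stated figure nearly survives.

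**Starters are not wholly lost.** This also stands. A reader might take the evaluable number to be 319 minus starters. The planned MMRM uses their pre-medication visits, so the no-recovery column is a worst case and not the planned analysis. Because 319 is already net of dropout, subtracting every starter would also count twice anyone who started and then withdrew.

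**Covariates could restore precision.** This is possible: baseline score, SBR, subtype and prior medication are in the model, while 10.64 is used as a raw SD. The SAP does not quantify any gain, so none can be credited.

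**Dropout might have been meant to include starters.** Nothing says so. Section 5.3.2.3 shows that medicated subjects continue to be assessed.

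**The printed effect is larger.** At 4.8 points with 50% starting and starts spread over the year, power is about 0.65 to 0.75 with MMRM recovery. That difference is also not the one that reproduces the plan's 80%.

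**Restating power changes no test or estimate.** This is true, and the OFF-state sensitivity analysis and the Week 72 analysis both use post-medication data. They do not make the Week 52 power statement correct.

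**Conclusion.** Wrong as written. The stated 80% reproduces with dropout as the only loss, while the Week 52 primary estimand removes a second set of data that Section 4 ignores. The direction is certain once any subject starts PD medication before Week 52; the size is not.

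At two-sided 0.05, a 4.4-point maximum effect and SD 10.64, assumed start rates of 20% to 60% give 0.73 down to 0.44 with no recovery and 0.78 down to 0.67 with half recovery. In none of the cases examined at 4.4 points with half or more starting does power reach 80%. The 0.04 allocation takes a further 3 to 4 points. The 89% must also fall, but by how much cannot be derived, because the SAP does not give the correlation between the Week 52 and Week 72 tests.

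The text supports neither a single power figure for the trial nor the claim that most Week 52 data are lost.

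**What to change.** 1. Reconcile Sections 4.3.1 and 4.3.2 of the extension SAP on when most subjects are expected to start PD medication.
2. Take the blinded pooled proportion who started PD medication before their own Week 52 assessment. It is obtainable, since Section 6 of the Year 1 SAP says that all subjects have completed Week 52. Count subjects who both started and dropped out once only.
3. Recompute Table 4.3 and the Week 52 power for the planned MMRM at alpha 0.04, stating the assumed visit pattern and covariance. Restate the 80% and 89% figures, and settle whether the maximum effect is 55% or the 60% implied by the printed means.
4. Report the number of unmedicated Week 52 observations per arm beside the primary result.

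The cost is one blinded count, a rerun of the power calculation and SAP wording. The downside is a lower stated power. No patients are added, and the primary test and estimand stay as they are.
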